## 4.3.2 Participant Eligibility

The eligibility criteria are broad in order to maximize the generalizability of the trial findings.

- Inclusion criterion:
  - Adults ≥18 years
  - Undergoing 3 times weekly in-center hemodialysis and having received dialysis treatment for at least 3 months
  - Able to provide informed consent
- Exclusion criteria:
  - Females who are pregnant or who plan to become pregnant while in the study
  - Calciphylaxis
  - o Nocturnal in-center dialysis

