## 7. SAFETY ASSESSMENTS

## 7.1 Adverse Event Reporting and Follow-up

Among patients undergoing hemodialysis, adverse events of moderate or higher severity are extremely common and usually result in hospitalization (or death). Based on this information, and given that hospitalization is the primary outcome of HiLo, additional information on adverse events will not be collected. Periodically reports will be generated related to laboratory-based events and allow the DSMB to review in a blinded manner the rates of these events in high versus low target groups. All laboratory parameters are measured either monthly or quarterly for all patients as part of routine clinical care:

- Hypophosphatemia, defined as serum phosphate <2.0 mg/dL;
- Hyperphosphatemia, defined as serum phosphate >7.5 mg/dl;
- Hypercalcemia, defined as total uncorrected serum calcium >10.5 mg/dL;
- Excessive iron supplementation, defined as serum ferritin >1000 ng/ml and transferrin saturation (TSAT) >50% (to assess for the potential effects of excess iron-based binder use); and
- Secondary hyperparathyroidism, defined as parathyroid hormone (PTH) levels 9 times the upper limit of normal for the assay, based on the threshold articulated in the international KDIGO guidelines.

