4.6.2 Clinical Safety Laboratory Events

Laboratory measurements are collected either monthly or quarterly for all patients as part of routine clinical care. Predetermined laboratory safety events will be collected. Below are defined the laboratory events of interest in HiLo:

- Hypophosphatemia, defined as serum phosphate <2.0 mg/dL
- Hyperphosphatemia, defined as serum phosphate >7.5 mg/dL
- Hypercalcemia, defined as total uncorrected serum calcium >10.5 mg/dL
- Excessive iron supplementation, defined as serum ferritin >1000 ng/mL and transferrin saturation (TSAT) >50%
- Secondary hyperparathyroidism, defined as parathyroid hormone (PTH) levels greater than 9 times the upper limit of normal for the assay

A listing of laboratory safety events will be created, along with a table of counts of each type of event by treatment group.

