5. CONVENTIONS

5.1 **Baseline Measurements**

Unless specified otherwise, a baseline value is the last assessment taken prior to the first dialysis session after consent. When there is a missing baseline assessment, it will not be imputed, thus, patients will be excluded from any changes from baseline analysis for which they have a missing baseline value.

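### Laboratory safety events are defined by a cut-off alone, so the by-arm table mixes abnormalities carried over from baseline with new ones

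*Protocol*

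**What the plan says.** Protocol 7.1 lists five laboratory events (hypophosphatemia, hyperphosphatemia, hypercalcemia, excessive iron supplementation and secondary hyperparathyroidism). Each is a value past a cut-off, for example "Hyperphosphatemia, defined as serum phosphate >7.5 mg/dl" and "Secondary hyperparathyroidism, defined as parathyroid hormone (PTH) levels 9 times the upper limit of normal for the assay". SAP 4.6.2 repeats the list, with PTH worded as "Secondary hyperparathyroidism, defined as parathyroid hormone (PTH) levels greater than 9 times the upper limit of normal for the assay". Neither document asks for a value on the normal side of the cut-off at baseline, a worsening from baseline, or a first occurrence.

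The planned output in SAP 4.6.2 is: "A listing of laboratory safety events will be created, along with a table of counts of each type of event by treatment group". Protocol 7.1 says the periodic reports will "allow the DSMB to review in a blinded manner the rates of these events in high versus low target groups". Neither states whether participants or measurements are counted, or over what denominator.

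Protocol 4.3.2 says "The eligibility criteria are broad in order to maximize the generalizability of the trial findings". Participants must have had at least 3 months of dialysis, and no criterion concerns phosphate, calcium, PTH, ferritin or TSAT. SAP 5.1 provides a usable reference point ("a baseline value is the last assessment taken prior to the first dialysis session after consent"), but SAP 4.6.2 does not refer to it.

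**The concern.** Participants are established dialysis patients, and Protocol 1.1 describes hyperphosphatemia as near-universal in this disease. Some will therefore enter already past a cut-off. SAP 4.6.2 notes that "Laboratory measurements are collected either monthly or quarterly for all patients as part of routine clinical care", so an abnormality that persists will be seen again soon after entry and will meet the event definition.

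The table would then add together two things: new abnormalities arising under the assigned target, and old ones that have not resolved. Both documents say that no further adverse-event information will be collected. Apart from the endpoint events themselves, and survey data that another institution analyses, this table is the main safety comparison available to the DSMB and the final report. As planned, it cannot show whether assignment to a target produced new abnormalities.

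**Working it through.** The documents give no laboratory-event rate, baseline prevalence or safety power, so there is no stated figure to reproduce. The calculation below is an illustration.

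**Inputs from the documents.** 1,900 participants per arm (Protocol 5.3, individually randomized phase); 1:1 allocation (Protocol 4.5); two-sided 0.05 (SAP 4.1).

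**Assumptions.** Baseline prevalence b; chance q that a baseline abnormality is seen again on study; new-event risk p of 10% in Lo and 13% in Hi among those not past the cut-off at baseline; each participant counted once.

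**Formulas.** Risk in an arm, all participants counted: P = b·q + (1 − b)·p. New events only: risk p, with n = 1,900·(1 − b) per arm. Power ≈ Φ(z − 1.96), with z = (P_Hi − P_Lo) / √{[P_Lo(1 − P_Lo) + P_Hi(1 − P_Hi)]/n}.

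**Case 1: equal and full persistence (q = 1 in both arms).**

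| b | P_Lo | P_Hi | Difference | Ratio | Power, all events | n per arm, new only | Ratio, new only | Power, new only |
|---|---|---|---|---|---|---|---|---|
| 5% | 14.5% | 17.35% | 2.85 points | 1.20 | 67% | 1,805 | 1.30 | 81% |
| 10% | 19.0% | 21.7% | 2.70 points | 1.14 | 54% | 1,710 | 1.30 | 79% |
| 15% | 23.5% | 26.05% | 2.55 points | 1.11 | 44% | 1,615 | 1.30 | 76% |

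Example at b = 10%: P_Lo = 0.10 + 0.90 × 0.10 = 0.190; P_Hi = 0.10 + 0.90 × 0.13 = 0.217; 0.217/0.190 = 1.14. Of the Lo-arm participants with an event, 0.10/0.190 = 53% were already past the cut-off at baseline. With q = 0.8 in both arms, power for all events is 69%, 58% and 48%, so the loss does not depend on complete persistence.

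**Case 2: persistence differs by arm.** Take q = 0.8 in Lo and 1.0 in Hi, with b = 10%. P_Lo = 0.08 + 0.09 = 0.170; P_Hi = 0.10 + 0.117 = 0.217. The difference is 4.7 points, the ratio 1.28 and power 96%, against 3.0 points, 1.30 and 79% for new events only. With q = 0.7 and 1.0 at b = 20%, P_Lo = 0.14 + 0.08 = 0.220 and P_Hi = 0.20 + 0.104 = 0.304, a difference of 8.4 points and a ratio of 1.38, above the new-event ratio.

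**Case 3: no difference in new events.** Take p = 10% in both arms, q = 0.8 (Lo) and 1.0 (Hi), b = 20%. P_Lo = 0.16 + 0.08 = 0.24; P_Hi = 0.20 + 0.08 = 0.28. The table shows a 4-point difference and a ratio of 1.17, and a two-sided 0.05 test would be significant about 80% of the time. All of that contrast is non-resolution of old cases.

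**Which case fits which event.** Protocol 4.6.7 leaves secondary hyperparathyroidism to usual care in both arms, so similar persistence, and hence Case 1, is most plausible for PTH. For phosphate the arms are meant to differ: Protocol 4.6 titrates Lo to below 5.5 mg/dl and aims for 6.5 mg/dl or more in Hi. Cases 2 and 3 are the likely pattern there.

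**The case against.** The strongest reply is that an all-events comparison by assigned arm is a legitimate randomized comparison. Failure to resolve can itself be an effect of the target, and in Case 2 restricting to new events would lower power from 96% to 79%. That stands. It is a reason to keep the planned table and add to it; replacing it would be a debatable change of estimand.

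A reader might infer that carried-over cases dilute any excess in Hi. The documents do not support this. Randomization balances prevalence at entry but not later persistence, and Cases 2 and 3 go the other way. A reader might also name hypercalcemia as a masked Hi-arm harm. Protocol 6.1.2 links it to calcium-based binders, so less binder use in Hi points, if anything, to an excess in Lo.

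Even in Case 1 the excess in participants is not hidden: at b = 10% it is 1,900 × 0.027 ≈ 51 counted either way (1,710 × 0.03 ≈ 51). The ratio and the precision suffer. The power figures concern a test that the SAP does not plan.

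Nor do the documents say that values measured before randomization are counted, or that a participant is counted again at each measurement. The unit is simply not stated. Finally, SAP 7 defers the output layout to a separate document and the DSMB works under a charter, neither of which is available here. A shift table may be specified in one of them. That limits how firmly the omission can be asserted, but the definitions in Protocol 7.1 and SAP 4.6.2 still carry no baseline condition.

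**Conclusion.** The concern holds in a limited form. As written, the laboratory table combines new abnormalities with those present at baseline that persist or recur, and it cannot separate them. With similar persistence in both arms (most plausible for PTH), the ratio is pulled from 1.30 to 1.20–1.11 at 5–15% baseline prevalence, and illustrative power is 67–44% instead of 81–76%. With unequal persistence (likely for hyperphosphatemia), the table confounds non-resolution with new onset and can enlarge the contrast, or create one where new-event risks are equal.

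These sizes rest on assumed prevalence, new-event risks and persistence, none of which the documents give. The direction is event-specific and cannot be stated for all five together. The primary analysis is not affected. This is a cheap improvement to safety reporting; it does not invalidate the plan.

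**What to change.** Keep the planned all-events table by assigned arm. Add the following to SAP 4.6.2 and to the DSMB reports under Protocol 7.1:

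- **New-onset events.** By arm, the number of participants who meet the definition on study among those who did not meet it at the SAP 5.1 baseline, each counted once, with the denominator stated.
- **Shift table.** By arm, baseline category against worst on-study category for each analyte, with a row for baseline unknown, so that persistence and worsening remain visible.

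State the counting unit and denominator for the all-events table too, and reconcile counts (SAP) with rates (Protocol) and the two PTH wordings.

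The data are already collected, so the cost is SAP wording and a little programming. There are two drawbacks. Participants without a baseline value drop out of the new-onset comparison. Because baseline is a single value, and PTH is collected only once every 3 months, some participants who fluctuate around a cut-off will be misclassified as new, so the recovery to a ratio of 1.30 in the illustration is a best case.

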## 8. STATISTICAL ANALYSIS PLAN AND DETERMINATION OF SAMPLE SIZE

## 8.1 Sample Size

The primary analysis of HiLo is the comparison of rank sum scores on the hierarchical composite endpoint of time to all-cause mortality and hospitalization rate. Simulations were employed to estimate the power of the planned analysis. The assumptions for the simulation include:

- 48-month study with a 24-month enrollment period
- Annual loss to follow-up rate of 5%
- 15% annual mortality rate in the standard of care arm and a hazard ratio of 0.85 comparing the intervention arm to the standard of care arm
- 35% of participants are "non-susceptible" to hospitalizations (will not have any hospitalizations during the course of the study).
- In the susceptible population, an average of 1.8 hospitalizations per year in the standard of care arm and 1.53 hospitalizations per year in the intervention arm (15% difference).

1000 different study populations with 3800 participants were simulated under the above assumptions and analyzed using the planned analysis method. The power was estimated as the percentage of significant results out of the 1000. The results of the simulation provided an estimated power above 95%. Under these same assumptions, there would be at least 80% power to detect a treatment difference for both mortality and hospitalization when analyzed as separate endpoints. These results indicate that the trial will have sufficient power to detect a treatment effect with a population size of 3800 participants.

## 8.2 Statistical Design

In the primary analysis of efficacy, the intention to treat (ITT) sample will be used that includes all randomized patients.

## 8.3 **Primary Outcome Analysis**

The primary outcome for HiLo is the hierarchical composite endpoint of time to all-cause mortality and the all-cause hospitalization rate in that order. Participants will have a rank score calculated using all pairwise comparisons and subsequently tested by the method proposed by Finkelstein and Schoenfeld. Participants will be hierarchically compared first on time to all-cause mortality, and compared on hospitalization rate only if the mortality comparison is not possible (e.g., both participants in an individual comparison survive throughout the follow-up period).

## 8.4 Major Secondary Analyses

The other main secondary outcome for HiLo is time-to-all-cause death, which will be compared between the serum phosphate treatment arms. Standard Cox regression methods will be employed to estimate the effect of phosphate treatment arm on time-to-all-cause death.

## 8.5 Other Planned Secondary Analyses

As an alternative approach to analyzing the secondary outcome of hospitalization, the analysis will be repeated after substituting individual participants' total number of days spent in the hospital per total length of follow-up in HiLo. Additional secondary outcomes related to nutrition are change from baseline in serum albumin, and PCR. Mixed effect models will be used for all available longitudinal observations in the ITT population to compare change from baseline in these secondary continuous variables between the two arms. Supplemental analyses will consider the "as treated" sample.

## 8.5.1 Interim Analyses

One interim analysis will be completed when 50% of patients have been enrolled and have at least 24 months of median follow-up time accrued to assess efficacy on the primary outcome. Throughout the trial, the mean separation in serum phosphate between the treatment groups will be continuously monitored, targeting a mean separation of at least 0.75 mg/dL and ideally, a mean separation of at least 1.0 mg/dL.

## 9. DATA AND SAFETY MONITORING

## 9.1 Data and Safety Monitoring Board

The NIDDK will convene a Data and Safety Monitoring Board (DSMB) to oversee the HiLo Trial. The DSMB will include individuals with expertise in dialysis, nutrition, clinical trials, and biostatistics. Members of the DSMB will not be involved in the conduct of the trial. The DSMB will review trial progress, data quality, blinded reports of rates of laboratory-based events in the high versus low target groups, and safety throughout the course of the trial in accordance with a Data and Safety Monitoring Board Charter. The DSMB will meet regularly and make recommendations to NIDDK about study progress, safety and trial continuation. DSMB reports will be submitted to the central Institutional Review Board (IRB).

## 9.2 Stopping Rules

The DSMB can make recommendations to stop the trial based on safety or other concerns. There will be no pre-specified stopping rules for efficacy or futility, however the DSMB will review the results of the interim analysis (see Section 8.5.1) with the following being considered:

- Futility of serum phosphate separation
- Futility of enrollment

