## 5.3 Participant Enrollment

Since HiLo includes a phosphate target that differs from current practice guidelines, the greater-than-minimal-risk research requires individual-level consent. HiLo initially used a cluster-randomized design in which participating dialysis centers were randomized to either the intervention or control arm. After completing enrollment in 30 dialysis units (14 Hi and 16 Lo sites), there was concern for biased enrollment. Therefore, the remainder of the trial will utilize individual-level randomization to ensure that arm assignment does not influence patients' willingness to participate. Patients enrolled in the cluster-randomized design will remain in the study through completion. For the individual randomized phase, the HiLo study will randomize approximately 3,800 additional participants (1,900 per arm).

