4.1.1 Control of Type I Error

To account for repeated significance testing of the accumulating data, the group sequential method of Lan and DeMets will be used as a guide for interpreting interim analyses. Monitoring boundaries for the primary endpoint will be based on a two-sided symmetric O'Brien-Fleming type spending function with an overall two-sided significance level of α =0.05. The O'Brien-Fleming approach requires large critical values early in the study but relaxes (i.e., decreases) the critical value as the trial progresses. A single planned interim analysis using alpha spending will be targeted to occur after the first 2000 to 2400 subjects have been enrolled with at least 24 months of median follow up time accrued. Additional interim analyses are not currently planned but may be performed upon request by the Data Safety and Monitoring Board (DSMB).

Assuming that the interim analyses take place as currently planned with just a single analysis after ~50% of subjects have been enrolled with at least 24 months of median follow up time accrued, the critical p-value for the test of the null hypothesis of no difference at the first interim analysis will be 0.001 and a result of |z| <3 or p>0.001 would suggest that the trial should continue. In order to maintain the overall 5% significance level of the trial, the critical p-value for declaring there to be a significant difference in the primary endpoint at the final analysis will be decreased from 0.05 to 0.049. However, the critical p-values for the interim analysis can be adjusted appropriately if additional interim analyses are requested by the DSMB.

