4.7 Interim Analysis

An interim analysis is planned for this trial when 50% of planned patients have enrolled with at least 24 months of median follow-up time accrued.

The interim analysis will investigate for futility at two possible levels: futility of enrollment, futility of serum phosphate separation (inability to sustain a separation of ≥ 0.75 mg/dl between arms).

A detailed interim analysis plan will be provided in a separate document.

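### Protocol and SAP disagree on whether the single interim look carries an efficacy decision, and the SAP's efficacy boundary contradicts itself

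*Protocol*

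**What the plan says.** Five sections describe the look or the final test that depends on it.

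- **Protocol 8.5.1** plans one interim analysis, at 50% enrollment with a median follow-up of at least 24 months, "to assess efficacy on the primary outcome".
- **Protocol 9.2** refers back to that analysis but says "There will be no pre-specified stopping rules for efficacy or futility". It names two matters for the DSMB to consider: "Futility of serum phosphate separation" and "Futility of enrollment".
- **SAP 4.1.1** applies Lan-DeMets monitoring to the primary endpoint, with a two-sided O'Brien-Fleming-type spending function at overall 0.05, and calls it a guide. It says that "the critical p-value for the test of the null hypothesis of no difference at the first interim analysis will be 0.001", pairs this with |z| = 3, and reduces the final critical p-value to 0.049. The look is to come "after the first 2000 to 2400 subjects have been enrolled".
- **SAP 4.5.1** declares a difference on the primary endpoint at p below 0.05.
- **SAP 4.7** says: "The interim analysis will investigate for futility at two possible levels: futility of enrollment, futility of serum phosphate separation". It sets 0.75 mg/dl as the separation limit, does not mention efficacy, and leaves details to a separate plan.

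SAP 6 states that no analysis departs from the protocol.

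**The concern.** A pre-specified critical value that reduces the final significance level is a pre-specified efficacy criterion, even if it is advisory. It cannot stand beside a protocol statement that no such rule exists. The protocol disagrees with itself (8.5.1 against 9.2), the SAP disagrees with itself (4.1.1 against 4.7 and 4.5.1), and the two documents disagree with each other while SAP 6 reports no difference.

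If the composite crossed the boundary, SAP 4.1.1 would point towards stopping, whereas Protocol 9.2 offers no criterion. In an open-label trial whose endpoint includes mortality, this should be settled before anyone sees comparative data. At the end of the trial, a p-value between 0.049 and 0.05 would be significant under SAP 4.5.1 and not under SAP 4.1.1.

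**Working it through.** **Inputs.** From SAP 4.1.1: overall two-sided alpha 0.05, O'Brien-Fleming-type spending, one interim look, interim criteria p = 0.001 and |z| = 3, final p = 0.049. From SAP 4.5.1: final p = 0.05. The information fraction t is not stated. I assume t = 0.50, because the SAP speaks of about 50% of subjects, and show a range.

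**Step 1: reproduce the boundary at t = 0.50.** The cumulative spend per side is 2[1 − Φ(z(0.0125)/√t)].
- z(0.0125) = 2.2414, and 2.2414/√0.50 = 3.170.
- Spend per side = 2[1 − Φ(3.170)] = 0.00153, so the interim critical |z| = 2.963 and the two-sided p = 2 × 0.00153 = 0.0031.
- Solving for the final critical value from the bivariate normal with correlation √0.50 gives 1.969, a two-sided p of 0.0490.

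The final 0.049 reproduces, and |z| = 3 is 2.963 rounded. The interim p of 0.001 does not reproduce.

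**Step 2: compare the two interim criteria.**
- |z| = 3: two-sided p = 2[1 − Φ(3)] = 0.0027 (one-sided 0.00135).
- Two-sided p = 0.001: |z| = 3.29.

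For p between 0.001 and 0.0027, the |z| criterion is crossed and the p criterion is not. The value 0.001 matches |z| = 3 only as a rounded one-sided p.

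**Step 3: could another information fraction explain 0.001?**

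| t | interim \|z\| | interim p | final p |
|---|---|---|---|
| 0.40 | 3.357 | 0.0008 | 0.0497 |
| 0.45 | 3.144 | 0.0017 | 0.0494 |
| 0.50 | 2.963 | 0.0031 | 0.0490 |
| 0.55 | 2.806 | 0.0050 | 0.0484 |
| 0.60 | 2.669 | 0.0076 | 0.0476 |

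An interim p of 0.001 arises at t of about 0.41, where the final level would be about 0.0497. No single t gives both 0.001 and 0.049.

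**Step 4: overall two-sided type I error at t = 0.50.**

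| Interim criterion | final 0.049 (SAP 4.1.1) | final 0.05 (SAP 4.5.1) |
|---|---|---|
| p = 0.001 | 4.92% | 5.02% |
| \|z\| = 3 | 4.99% | 5.08% |
| \|z\| = 2.963 | 5.00% | 5.10% |

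Holding these criteria fixed and varying t from 0.40 to 0.80, the overall error runs from 4.90% to 5.14%. If no efficacy test is done, no alpha is spent: a final test at 0.05 has error 5%, and one at 0.049 gives up 0.1 percentage point for nothing.

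**Step 5: the trigger.** The midpoint of 2000 to 2400 is 2200, and 2200/4400 = 50%. The range is 2000/4400 = 45.5% to 2400/4400 = 54.5%. Half of the individually randomized cohort would be 3800/2 = 1900. Protocol 5.3 says "the HiLo study will randomize approximately 3,800 additional participants (1,900 per arm"). SAP 4.5.3 would analyze the cluster-phase participants separately, if at all, while SAP 2.1.1 puts every consented patient in the ITT population. Neither Protocol 8.5.1 nor SAP 4.1.1 says whose enrollment and median follow-up count.

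**The case against.** The strongest reply is that a guideline is not a stopping rule. SAP 4.1.1 calls the method a guide and uses advisory language, so Protocol 9.2 may mean only that nothing is binding. Protocol 9.2 also cross-refers to 8.5.1, does not say that its two futility items are exhaustive, and lets the DSMB recommend stopping for safety or other concerns. It follows that the boundary can be non-binding and that the DSMB would see the efficacy result. The conflict remains, because a non-binding boundary is still pre-specified and the final level is lowered to pay for it.

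On the two interim criteria, SAP 4.1.1 joins them with an or. Read literally, meeting either one favors continuing, and the rule collapses to p = 0.001. That reading makes |z| = 3 redundant, and at t = 0.50 the Lan-DeMets calculation agrees with |z| = 3 rather than with 0.001.

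A reader might draw four stronger conclusions that the documents do not support.
- *The DSMB cannot know what the look decides.* Protocol 9.1 cites a charter and SAP 4.7 a separate interim plan. Neither was available, and either may settle the matter in practice.
- *Type I error is materially inflated.* It is not, as Step 4 shows.
- *The 0.75 mg/dl figure conflicts.* Protocol 8.5.1 and SAP 4.7 give the same value. It is a monitoring target in one and a futility limit in the other.
- *The trigger is not about 50%.* It is centered on half of 4400. Only the choice of cohort is left open.

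**Conclusion.** The point holds as an inconsistency in the decision rule. Protocol 8.5.1 and 9.2 and SAP 4.1.1, 4.5.1 and 4.7 cannot all describe the same look and final test, and SAP 6 does not acknowledge the difference. Within SAP 4.1.1 the two interim criteria differ by 0.29 on the z scale (3.29 − 3.00) and give different signals for p between 0.001 and 0.0027. The final level is 0.049 in one section and 0.05 in another.

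The cost in type I error is small: 4.9% to 5.1% at an assumed information fraction of 0.50, and much the same from 0.40 to 0.80. The p-value comparison with |z| = 3 needs no assumption about information. The Lan-DeMets values do, and should be recomputed at the actual fraction. The charter and interim plan could supply the working rule, but they would not correct the protocol and SAP text.

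**What to change.** Before the look, choose one of two courses and carry it through every section.

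**(a) Keep the efficacy look.** Amend Protocol 9.2 to cite the SAP 4.1.1 boundary as a non-binding efficacy guideline. Add the efficacy test to SAP 4.7. State a single interim criterion: for Lan-DeMets O'Brien-Fleming-type spending at t = 0.50, |z| of about 2.96, two-sided p of about 0.003 and final p of 0.049, all recomputed at the actual information fraction. Replace 0.05 with the adjusted final level in SAP 4.5.1. The present 0.001 and |z| = 3 pair should not be copied into the protocol.

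**(b) Drop the efficacy look.** If no early efficacy decision is intended, remove the efficacy purpose from Protocol 8.5.1 and the boundary from SAP 4.1.1, make no unblinded comparison of the primary outcome at that look, and test the final analysis at 0.05.

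Under either course, state which cohort, all of the roughly 4400 or the 3,800 individually randomized, sets the 50% enrollment and 24-month median follow-up trigger, so that it matches the cohort of the primary analysis.

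The cost is a short protocol amendment, a few SAP sentences, and matching wording in the charter and interim plan. No change to data collection or sample size is needed.
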